6.2 Per Protocol Set (PPS)

The PPS refers to the set of subjects who meet the inclusion criteria and complete the research project, which also means they comply with the research protocol, have good compliance, do not use banned substances during trial, and have completed the case report form (CRF). The PPS analysis is mainly used to assess primary efficacy.

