2.4. The following individuals will be considered as lost to follow-up: first, patients who suddenly present serious physical or mental diseases (not related to the study) during the study period, such as malignant tumors, severe mental illness, traffic accidents, etc.; second, patients who have serious side effects in which the symptoms can be relieved by discontinuing the study medication; third, patients who actively ask to stop using the study medication or refuse to come to follow up visits. Fourth,

patients who need to take other medications due to the development of other new diseases, where the new medications may interfere with the study results, such as hypoglycemic agents, including insulin.

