### 3. Assignment and intervention:

#### 3.1. Calculation of the sample size and the method of assignment:

Sample size calculation: A total of 196 patients will be enrolled in this study. The sample size is estimated as follows:

Previous studies have reported that the efficiency rate of metformin and simvastatin in the treatment of NAFLD is 36-52%. The investigators hypothesize that the efficiency rate of Compound Zhenshu Tiaozhi capsules will increase by 25% compared to standard drugs.

Statistical calculation:  $P_1 = 69\%$ ,  $P_2 = P_3 = 44\%$ ,  $P_4 = 10\%$ ,  $\delta = P_1 - P_2 = 25\%$ , with  $\alpha = 0.05$ , power = 0.80, and a bilateral test, of which  $w = \sqrt{\frac{\sum_{i=1}^m (P_{t,i} - P_{c,i})^2}{P_{c,i}}}$ , thus n will be equal to 44. Assuming that the rate of loss to follow up is 10%, each group will require 49 cases. Therefore, a total of 196 cases will be required for the four groups.

3.2 The method of assignment: [name], a staff member working in the Department of Statistics in Guangdong Pharmaceutical University, is responsible for generating random sequences using the SAS software. A total of 196 numbers from 1 to 196 will be randomly generated (Supplement 2). Newly diagnosed patients who meet the inclusion criteria will have a case number according to their order of enrollment (for example: case number of the first patient: 001, second patient: 002). They will then obtain the corresponding therapeutic regimens based on their case number with 1:1:1:1 ratio randomized tables. The first group is the TLC group; the second group is the TLC + metformin group (0.5 g, PO tid); the third group is the TLC + Compound Zhenzhu Tiaozhi capsules group (2.52 (four tablets), PO tid); the fourth group is the TLC + simvastatin group (20 mg, PO qn).

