4.4. To evaluate the therapeutic effects of Compound Zhenzhu Tiaozhi capsules on NAFLD

1) To assess whether the content of intrahepatic fat will decrease after 1 month, 3 months, and 6 months of Compound Zhenzhu Tiaozhi capsule therapy.

i. Compare the therapeutic effects of Compound Zhenzhu Tiaozhi capsules at 1 month, 3 months, and 6 months with the baseline (pre-vs.post-therapeutic effects of Compound Zhenzhu Tiaozhi capsules).

ii. Compare the therapeutic effects in the Compound Zhenzhu Tiaozhi capsule group with that of the other three groups at parallel time points (Compound Zhenzhu Tiaozhi capsules vs. Conventional drugs).

2) To assess whether NAFLD-FS will be alleviated after 1 month, 3 months, and 6 months of Compound Zhenzhu Tiaozhi capsule therapy.

i. Compare the therapeutic effects of Compound Zhenzhu Tiaozhi capsules at 1 month, 3 months, and 6 months with the baseline (pre- vs. post-therapeutic effects of Compound Zhenzhu Tiaozhi capsules).

ii. Compare the therapeutic effects in the Compound Zhenzhu Tiaozhi capsule group with those of the other three groups at parallel time points

(Compound Zhenzhu Tiaozhi capsules vs. Conventional drugs).

3) To assess whether insulin resistance will be improved after 1 month, 3 months, 6 months of Compound Zhenzhu Tiaozhi capsule therapy.

- i. Compare the therapeutic effects of Compound Zhenzhu Tiaozhi capsules at 1 month, 3 months, and 6 months with the baseline (pre- vs. post-therapeutic effects of Compound Zhenzhu Tiaozhi capsules).
- ii. Compare the therapeutic effects in the Compound Zhenzhu Tiaozhi capsule group with those of the other three groups at parallel time points (Compound Zhenzhu Tiaozhi capsules vs. Conventional drugs).

4) To assess whether the lipids profile in peripheral blood and liver biochemical parameters (ALT, AST, GGT) will be reduced after 1 month, 3 months, and 6 months of Compound Zhenzhu Tiaozhi capsule therapy.

- i. Compare the therapeutic effects of Compound Zhenzhu Tiaozhi capsules at 1 month, 3 months, and 6 months with the baseline (pre- vs. post-therapeutic effects of Compound Zhenzhu Tiaozhi capsules).
- ii. Compare the therapeutic effects in the Compound Zhenzhu Tiaozhi capsule group with those of the other three groups at parallel time points (Compound Zhenzhu Tiaozhi capsules vs. Conventional drugs).

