3.1. Design

This is a prospective, open-label and randomized clinical study.

[figure not shown]

Group 1: treatment with Compound Zhenzhu Tiaozhi capsules

Group 2: treatment with simvastatin

Group 3: treatment with metformin

Group 4: TLC (transform life custom)

ALT, alanine transaminase; ASCVD, atherosclerotic cardiovascular disease

Biochemical tests include routine blood test, liver function tests including measurement of transpeptidases, uric acid, FBS (fasting blood glucose), FINS (fasting insulin), and lipid profiles.

Physical examinations include waist circumference, hip circumference, blood pressure, heart rate, and body mass index (BMI).

Imaging include abdominal color doppler ultrasound, and Fibrotouch

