3.4 Sample Size

A total of 196 patients will be enrolled in this study. The sample size is estimated as follows:

Previous studies have reported that the efficiency rate of metformin and simvastatin in the treatment of NAFLD is 36-52%. We hypothesize that the efficiency rate of Compound Zhenshu Tiaozhi capsules will increase by 25% compared to standard drugs.

Statistical calculation: $P_1 = 69\%$, $P_2 = P_3 = 44\%$, $P_4 = 10\%$, $\delta = P_1 - P_2 = 25\%$, with $\alpha = 0.05$,

power = 0.80, and a bilateral test, $n = \frac{\chi_{\alpha}^2 + \chi_{\beta}^2}{w^2}$, of which $w = \sqrt{\sum_{i=1}^m \frac{(P_{t,i} - P_{c,i})^2}{P_{c,i}}}$, thus n will be equal to 44.

Assuming that the rate of loss to follow up is 10%, each group will require 49 cases. Therefore, a total of 196 cases will be required for the four groups.

4. Evaluation of the Efficacy of Parameters and Predictors

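### SAP 6.2 makes compliant completers the main set for primary efficacy in an open-label superiority trial, and the supplied text does not rank the FAS/ITT analysis or the carry-forward rules against it

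*SAP*

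**What the plan says.** **Main set.** SAP 6.2 limits the PPS to eligible patients who finish the study, comply well, take no prohibited substances and have a completed case report form. It then says: "The PPS analysis is mainly used to assess primary efficacy". No other set in the supplied text is assigned to primary efficacy.

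**Design and aim.** SAP 3.1: "This is a prospective, open-label and randomized clinical study". SAP 3.4: "We hypothesize that the efficiency rate of Compound Zhenshu Tiaozhi capsules will increase by 25% compared to standard drugs". No non-inferiority margin is given, and the Protocol's expected results also look for superiority over simvastatin and metformin.

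**Expected loss.** SAP 3.4: "Assuming that the rate of loss to follow up is 10%, each group will require 49 cases".

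**Who counts as lost.** Protocol 2.4 lists four groups:
- serious illness unrelated to the study;
- "patients who have serious side effects in which the symptoms can be relieved by discontinuing the study medication";
- "patients who actively ask to stop using the study medication or refuse to come to follow up visits";
- new medication that may interfere with the results.

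It does not say whether patients who stop treatment are still measured.

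**Other analysis text.** SAP 6.1 builds the FAS from qualified and dropout cases, less exclusion cases that it does not define, and invokes ITT when the primary outcome is missing. SAP 9.3 gives four carry-forward rules and names no analysis set.

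**The concern.** A completer-and-complier set is chosen by what happens after randomisation. Three of the four Protocol 2.4 exits (side effects, asking to stop or refusing visits, interfering new drugs) can depend on treatment; unrelated illness is less likely to. In an open-label trial patients and staff know the arm when these events occur. The documents do not say who decides PPS membership or whether that person is masked.

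The exits are not the same in every arm. The TLC group is assigned no study medication (Protocol 3.2). As worded, leaving through drug side effects or by asking to stop the drug therefore cannot apply there. Yet Protocol 4.4 plans this comparison: "Compare the therapeutic effects in the Compound Zhenzhu Tiaozhi capsule group with that of the other three groups at parallel time points".

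If losses differ by arm and relate to response, the main result can favour either arm. With 6.1 and 9.3 left unranked, two analysts following the same SAP could also report different primary results.

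**Working it through.** **1. The rules side by side**

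| SAP 9.3 rule | Applies to | Fit with 6.2 |
|---|---|---|
| 1 | month-6 value missing, no response when therapy stopped | covers non-responders only |
| 2 | withdrew, still without response | only patients the PPS excludes |
| 3 | intermediate value missing, other measures present | does not supply month 6 |
| 4 | withdrew because fully recovered | only patients the PPS excludes |

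Rules 1, 2 and 4 depend on the outcome. A patient who is Effective under SAP 4.1 (down at least one level) but withdraws short of full recovery gets no month-6 value under any rule.

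**2. The plan's loss figure**

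44 / (1 − 0.10) = 48.9, so 49 per arm, and 4 × 49 = 196. At 10% loss 44 of 49 remain in each arm, so 4 × 5 = 20 of 196 leave. The inflation step reproduces. Whether 44 itself is right is a separate question. Poor compliance is not a Protocol 2.4 category, so exclusions for it would come on top of the 10%.

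**3. What selection could do under no true difference**

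*From the plan:* 49 per arm, two-sided α = 0.05, 44% response for the active drugs, 10% for TLC.

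*Assumed:* the loss split between arms; the response q of excluded patients; a pooled Z test at month 6 (the supplied text names no primary test and no single deciding visit).

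PPS response rate = (p − loss × q) / (1 − loss). Example with p = 0.44 and q = 0: at 20% loss 0.44/0.80 = 0.550; at 5% loss 0.44/0.95 = 0.463; shift 8.7 points.

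PPS n = 49 × (1 − loss), rounded: 49, 47, 45, 44, 43, 39 at 0, 5, 8, 10, 12, 20%. The table gives the exact binomial probability that |Z| > 1.96, by direction, with p = 0.44 in both arms. Nominal is 2.5% each way.

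| Loss (more v less) | q = 0: shift (points) | q = 0: arm losing more wins | q = 0: other arm wins | q = 22%: arm losing more wins | q = 44% (no bias): arm losing more wins |
|---|---|---|---|---|---|
| 10% v 10% | 0 | 2.2% | 2.2% | 2.3% | 2.4% |
| 12% v 8% | 2.2 | 3.6% | 1.4% | 2.8% | 2.2% |
| 10% v 5% | 2.6 | 5.1% | 1.6% | 4.0% | 3.1% |
| 10% v 0% | 4.9 | 6.4% | 0.8% | 3.9% | 2.3% |
| 20% v 5% | 8.7 | 12.2% | 0.3% | 5.9% | 2.6% |

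At q = 22% the shifts are 1.1, 1.3, 2.4 and 4.3 points for the four unequal splits. The last column is free of bias, so its departures from 2.5% come from discreteness. That matters most at 10% v 5%: of the 5.1%, 3.1% is present without any bias.

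**4. Capsule v TLC**

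With 10% response in both arms and q = 0, the arm losing more wins 2.9% of the time at 10% v 10%, 3.6% at 10% v 0% and 4.3% at 20% v 5%. The distortion is small there.

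**The case against.** **The ITT analysis is already planned.** SAP 6.1 keeps dropouts in the FAS, and 6.1 and 9.3 both address missing primary outcomes. Read together they suggest an FAS analysis with carry-forward, and the word mainly in 6.2 may only describe what the PPS is for. That reading is possible. It does not resolve the conflict: 6.1 does not say whether ITT is co-primary, sensitivity or fallback; the FAS drops undefined exclusion cases; 9.3 names no set; and only 6.2 assigns a set to primary efficacy.

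**The supplied SAP ends at 9.5 (baseline characteristics).** A later section might rank the sets. This stands as a limit on the statement that they are unranked. It does not change the wording of 6.2.

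**The numbers are assumptions and often modest.** This stands. Equal loss gives no inflation. At 12% v 8% with q = 0 the two directions sum to 3.59% + 1.41% = 5.0%, so only the balance between directions moves. The largest figure needs a 20% v 5% split with every excluded patient a non-responder. The primary measure is a FibroTouch reading, so open-label risk bears mainly on retention and PPS membership.

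**TLC patients can leave too.** True: refusing visits, new drugs and unrelated illness still apply to them, and the calculated effect in that comparison is small.

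**Counting missing as Invalid can mislead as well.** True, and the size is similar (see the fix). It is therefore not proposed as the sole remedy.

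**Conclusion.** Wrong as written, and to be corrected before analysis. This rests on SAP 6.2 making a set selected after randomisation the main basis for primary efficacy in an open-label trial that seeks superiority. It does not rest on any one loss scenario. Superiority is inferred from the 25-point hypothesis and the expected results; the documents do not use it as a design label, and open-label is stated only in the SAP.

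The direction of bias is unknown. Under 44% true response in both arms, the false-win rate for the arm losing more ranges from 2.2% (equal 10% loss) to 12.2% (20% v 5%, all excluded patients non-responders), against a nominal 2.5%. If excluded patients respond at 22%, the top of that range is 5.9%. If they respond like everyone else, there is no bias.

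Confidence is high on 6.2 itself. That the other rules are unranked holds for the text up to SAP 9.5.

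**What to change.** **SAP 6.** Make the analysis of all randomised patients in their assigned arm the primary efficacy analysis. Keep the PPS as a sensitivity analysis, with membership decided masked to arm and before database lock. State which set 9.3 serves.

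**Protocol 2.4.** Separate stopping treatment from loss to follow-up, and still invite patients who stop to the FibroTouch visits already planned at months 1, 3 and 6.

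**SAP 9.3.** Replace the outcome-dependent rules with one prespecified month-6 rule applied alike in all arms, plus a sensitivity analysis under a different missing-data assumption.

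**Cost.** Wording in both documents, one more sensitivity analysis, and effort to bring stopped patients back. The observed difference may shrink. Power for 69% v 44%, two-sided 5%, is Φ[(Δ − 1.96 × SE0)/SE1], with SE0 pooled and SE1 unpooled:
- 44 completers per arm: (0.25 − 1.96 × 0.1057)/0.1023 = 0.42, power 66%.
- 49 per arm, 10% in each counted Invalid (0.69 × 0.9 = 62.1% v 0.44 × 0.9 = 39.6%): (0.225 − 1.96 × 0.1010)/0.0984 = 0.27, power 61%.
- 49 per arm, every month-6 status obtained and those who stop responding at their arm's rate: (0.25 − 1.96 × 0.1002)/0.0969 = 0.55, power 71%.

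Exact values are 66%, 63% and 72%. The gap to 80% is mostly a separate sample-size problem.

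Missing-as-Invalid is one possible rule but is not neutral. With 44% response in both arms and missing patients truly responding at 44%, the arm with less missing data wins falsely 2.5% of the time at 10% v 10%, 3.7% at 12% v 8%, 6.6% at 10% v 0% and 9.8% at 20% v 5%. This is why continued measurement and the sensitivity analysis belong in the fix.

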6.3 Safety Set (SS)

SS analysis will be performed for all randomized subjects who received at least one dose of the study drugs and have at least one safety assessment. The missing value of safety cannot be carried forward. Some excluded cases can be evaluated, such as a case whose age exceeds the inclusion criteria, but will not include cases who use prohibited drugs. The rate of adverse events will be calculated using the total cases in the SS as the denominator.

7. Interim Analysis

Some specialized staff in the Department of Statistics will be responsible for the real-time statistical analysis of the study data and will present the results with an analysis report.

8. Data Verification

The final data analysis should not be started until all data have been verified, questions have been resolved, and the databases have been locked. We aim to demonstrate that the source of the data is real and valid, and will ensure that the database is locked prior to data analysis.

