#### 4. Prescriptions:

4.1: Medications: the dose of Compound Zhenzhu Tiaozhi capsules is 2.52 (4 tablets) tid; metformin is 0.5, tid, and simvastatin is 20mgqn. In general, subjects will be in the hospital for approximately 1 week and continue to receive treatment after discharge from the hospital. The total period of treatment will be 6 months.

4.2: Biochemical assessments: Patients will undergo all the following tests upon admission:

Routine blood test, tumor biomarker tests (alpha-fetoprotein [AFP], carcinoembryonic antigen [CEA], carbohydrate antigen 125 [CA125], and carbohydrate antigen 19-9 [CA19]), uric acid, liver function (representing hepatocyte injury: alanine aminotransferase, aspartate aminotransferase, leucyl aminopeptidase, glutamyl transpeptidase; representing liver secretory function: total bilirubin (TBS), direct bilirubin (DBIL), indirect bilirubin (IBIL); representing liver reserve function: total protein (TP), albumin (ALB), globulin (GLB), and the albumin to globulin ratio (A/G), serum lipid profile (triglyceride, very low density lipoprotein, total cholesterol, low density lipoprotein, high density lipoprotein), FINS (fasting insulin), fasting blood glucose, serum biomarkers of HBV ([i]Hepatitis B surface antigen [HBsAg]; [ii]Hepatitis B surface antibody [anti-HBs]; [iii]hepatitis B e antigen [HBeAg]; [iv]Hepatitis B e antigen antibody [anti-HBe]; [v]Hepatitis B core antibody [anti-HBc]), TP-Ab, syphilis serological test (TRUST), human immunodeficiency virus (HIV), hepatitis C virus antibody,

glycosylated hemoglobin, intestinal mucosal barrier function, coagulation test (prothrombin time [PT], activated partial thromboplastin time [APTT], thrombin time [TT], and fibrinogen [FIB]), Fibrotouch, hydrogen and methane breath test.

4.3 Medical advice on discharge: Physicians need to inform patients regarding the severity of complications in the late stage of NALFD and the importance of early treatment. All the patients should continue treatment after discharge and follow-up in the clinic. They will be required to come back to hospital one month later for re-assessment of the above mentioned items. The appointment telephone number is [name]. The contact doctor is [name].

4.4 All patients will be treated with TLC.

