4.3 Safety

Safety profiling includes adverse events and serious adverse events, as well as vital signs and laboratory tests.

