9.5 Baseline characteristics

According to the definition of SS, the demographic and baseline characteristics, as well as vital signs will be described. Qualitative data analysis includes the number of cases and composition ratios. Quantitative data analysis includes the number of cases, mean, standard deviation, median, maximum and minimum values, upper and lower quartiles (Q1 and Q3), and confidence interval. Chi-square test, rank-sum test, and univariate analysis will be used when appropriate.

Screening and baseline indicators are as follows:

Date of birth, gender, race, marital status, occupation, pregnancy test results, medical history, pathways of hepatitis infection, time of infection, and laboratory tests.

- History: changes to or any new combinations of medications
- Physical examinations

-
- Vital signs: blood pressure, pulse, heart rate, respiration, body temperature, height, weight, BMI
 - The physical examinations including skin, head, eyes, ears, nose and sinuses, mouth and pharynx, neck, back, breasts and armpits, chests and lungs, heart, abdomen, rectum and anus, reproductive organs, legs, musculoskeletal system, and blood vessels.
 - Urine indicators
 - pH, protein, glucose, acetone body, white blood cell (WBC) and red blood cell (RBC) counts
 - Hematology indicators
 - Routine blood test: hemoglobin, RBC, WBC, absolute neutrophil count, absolute lymphocyte count and classification, platelet count
 - Prothrombin time
 - Biochemistry tests: alanine transaminase (ALT), aspartate transaminase (AST), total bilirubin (Tbil), direct bilirubin (Dbil), total protein (TP), albumin (ALB), Gamma-glutamyl transferase (GGT), alkaline phosphatase (ALP), creatinine (Cr), glucose (Glu), triglyceride (TG), cholesterol (Cho), blood urea nitrogen (BUN) and (low density lipoprotein) LDL
 - Viral hepatitis biomarkers
 - Hepatitis B surface antigen and antibody (HBsAg, anti-HBs)
 - Hepatitis B e antigen and antibody (HBeAg, HBeAb)
 - Hepatitis B core antibody (HBcAb)
 - Human immunodeficiency virus (HIV)-Ab, HIV RNA
 - Hepatitis B virus (HBV) DNA
 - Hepatitis C virus (HCV) RNA
 - Serum alpha-fetoprotein (AFP) detection
 - Chest X-ray
 - Electrocardiogram (ECG)
 - Abdominal ultrasound
 - Left hepatic lobe (cm), right hepatic lobe (cm), sphincter diameter (cm), portal vein diameter (cm), spleen thickness (cm), spleen length (cm), and splenic vein diameter (cm)

-
- Quality of life
 - SIBO
 - Insulin resistance levels

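### The Safety Set requires a dose of study drug, so as written the lifestyle-only (TLC) arm, 49 of 196 patients, has no adverse event rate

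*SAP*

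**What the plan says.** **Entry rule.** SAP 6.3 forms the SS from "all randomized subjects who received at least one dose of the study drugs", provided they also have a safety assessment. It then fixes the denominator: "The rate of adverse events will be calculated using the total cases in the SS as the denominator".

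**Arms.** Protocol IV.3.2 sets out four arms. It says "The first group is the TLC group"; the other three receive TLC plus metformin, TLC plus the capsules, or TLC plus simvastatin. SAP 3.1 numbers the arms differently but describes the same lifestyle arm: "Group 4: TLC (transform life custom)".

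**What counts as a drug.** Under Prescriptions, the protocol's Medications item (4.1) names three products: "the dose of Compound Zhenzhu Tiaozhi capsules is 2.52 (4 tablets) tid; metformin is 0.5, tid, and simvastatin is 20mgqn". TLC is a separate item (4.4): "All patients will be treated with TLC". Its sub-items cover diet, weight, exercise, smoking and alcohol.

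**What the set feeds.** SAP 4.3 gives the scope of safety: "Safety profiling includes adverse events and serious adverse events, as well as vital signs and laboratory tests". SAP 9.5 also uses the set for baseline: "According to the definition of SS, the demographic and baseline characteristics, as well as vital signs will be described". SAP 6.1 places baseline and demographic analysis under the FAS.

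**The concern.** A dose-based entry rule suits a trial in which every arm takes a product. Here one arm does not. A programmer who derives the SS flag from dosing records will set it to zero for every TLC patient, and the SAP gives no other route into the set.

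That arm has a particular use for safety. Since all patients receive TLC, only the TLC-only arm shows how often events occur without any of the three drugs. Without it, adverse event rates in the drug arms can be compared with each other but not with a no-drug background. The other safety data in SAP 4.3 would lose the same arm if they were analysed in the SS; the SAP does not say which set they use. The baseline description in SAP 9.5 would have no TLC column.

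**Working it through.** **1. Does the TLC arm receive a study drug?** Neither document defines the term. The protocol's Medications item lists the capsules, metformin and simvastatin, and TLC stands apart from it as advice given to everyone. The advice mentions smoking-cessation medication as an option for all smokers, but this is not a trial product and is not specific to one arm. No TLC-only patient can therefore meet the dosing condition as written.

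**2. Planned arm size.** Inputs from SAP 3.4: 44 per group before losses, 10% loss to follow-up, four groups, 1:1:1:1 allocation.
- 44 / (1 − 0.10) = 48.9, rounded up to 49 per arm
- 4 × 49 = 196

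Both of the plan's figures are reproduced.

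**3. Safety Set under the written rule.**

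| | Planned | Maximum in SS as written | Maximum in SS after the fix |
|---|---|---|---|
| Three drug arms | 3 × 49 = 147 | 147 | 147 |
| TLC arm | 49 | 0 | 49 |
| Total | 196 | 147 (147/196 = 75%) | 196 |

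The share lost is 49/196 = 25%. The entries are maxima because each patient also needs a safety assessment and, in the drug arms, a dose.

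**4. What the arm could contribute.** As an illustration that assumes no event rate, take an event type never seen among *n* TLC patients. The exact two-sided 95% upper limit for its background rate is 1 − 0.025^(1/*n*). With *n* = 49 this is 1 − 0.025^(1/49) = 7.25%, or about 7.3%. With *n* = 0 there is no limit at all. The 7.3% describes what 49 patients can show; it does not measure an error in the plan.

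**5. Baseline.** SAP 6.1 puts baseline under the FAS, which is not defined by dosing and so can include the TLC arm. SAP 9.5 puts it under the SS, which under step 3 cannot. SAP 9.1 provides for descriptive analysis by FAS, PPS and SS, but under case distribution, and it does not say which set supplies the main baseline table.

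**The case against.** **The intent is plain.** The documents use the word drugs loosely. Protocol Endpoints 4.4 compares the capsules with all three other groups, TLC included, and labels this a comparison with conventional drugs. TLC appears under the Prescriptions heading, and SAP 3.2 and 3.3 speak of a therapeutic regimen for every enrolled patient. The use of the SS for baseline in SAP 9.5 also suggests that the authors thought it held all arms. This stands as evidence of intent, but none of it repairs the rule: no text counts TLC as a study drug or says when a TLC patient enters the set. The trial is open-label and SAP 7 provides for real-time analysis, so it is better to settle the definition in advance.

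**The literal reading is selective.** Read just as strictly, the denominator sentence gives one pooled total and no rate for any single arm. That is fair, and the fix should say that rates are by arm. It does not rescue the TLC arm, which contributes no patients to the set on either reading.

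**The consequence is small.** Much of this stands. SAP 2.2 names metformin and simvastatin as the safety comparators, and both are unaffected. No adverse event comparison with TLC is announced. Protocol Endpoints 4.4 still compares ALT, AST and GGT with all three other groups.

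**Conclusion.** The point holds as a modest wording error with a definite result. Under the rule as written, 0 of 49 TLC patients enter the SS, at most 147 of 196 (75%) remain, and the only arm without a drug has no adverse event rate. This rests on planned arm sizes and on the ordinary meaning of a dose of study drug. Confidence is high about the wording. It does not extend to a prediction that the arm would really be left out, since the intent was probably to include it.

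Four stronger readings are tempting, and the documents do not support them:
- *The trial's safety objective fails.* It does not: the comparison in SAP 2.2 is intact.
- *SAP 6.1 and 9.5 contradict each other.* Both descriptions could be produced, and 6.1 does not say that baseline is analysed only in the FAS. The missing TLC column in 9.5 follows from the SS definition and is not a separate error.
- *SAP 6.3 removes every user of prohibited drugs from the SS.* The subject of that clause is a group of otherwise excluded cases, so it most naturally limits which of them are re-admitted.
- *The relevant TLC count is 44 rather than 49.* The planned 10% loss does not reduce the SS in that way: a patient lost after a first safety assessment stays in it.

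**What to change.** In SAP 6.3, define the SS as all randomised patients who have a safety assessment after assignment and who either took at least one dose (the three drug arms) or were assigned to TLC (the TLC arm, with entry from the randomisation date). Then:
- state that adverse event rates use each arm's own SS total;
- list by arm the drug-arm patients who took no dose, because the entry rule cannot be identical in dosed and undosed arms;
- name the FAS of SAP 6.1 as the population for the main baseline table, and amend SAP 9.5 to match.

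The cost is a few sentences of SAP text, with no change to sample size or efficacy analysis. The randomisation date is preferable to a start-of-TLC date: the documents name no field for the latter, and SAP 3.3 mentions only case number and regimen as recorded. Using it should need no new data collection, provided the date of assignment is kept for each case.

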2.2 Primary Objectives

1. To explore the safety and efficacy of Compound Zhenzhu Tiaozhi capsules for the treatment of NAFLD, compared with metformin and simvastatin.
2. To summarize the regularity of disease progression in the development of NAFLD.
3. To promote the therapeutic options of NAFLD and to improve long-term efficacy.
4. To explore the potential mechanism of Compound Zhenzhu Tiaozhi capsules for the treatment of NAFLD.

[figure not shown]

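### SAP 6.3 bars users of prohibited drugs from the Safety Set, against its own first sentence; observed adverse events of dosed patients can then go uncounted and the adverse event rate can be biased

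*SAP*

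**What the plan says.** SAP 6.3 opens with an inclusive rule: "SS analysis will be performed for all randomized subjects who received at least one dose of the study drugs", subject to at least one safety assessment. It then deals with excluded cases: "Some excluded cases can be evaluated, such as a case whose age exceeds the inclusion criteria", and the sentence ends "but will not include cases who use prohibited drugs". It closes by fixing the denominator: "The rate of adverse events will be calculated using the total cases in the SS as the denominator".

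SAP 4.3 sets the scope of safety: "Safety profiling includes adverse events and serious adverse events, as well as vital signs and laboratory tests". It names no other population for these data.

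SAP 6.2 separately requires that Per Protocol patients took no banned substances during the trial. SAP 6.1 leaves exclusion cases out of the Full Analysis Set, without defining that term.

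The first primary objective in SAP 2.2 is "To explore the safety and efficacy of Compound Zhenzhu Tiaozhi capsules for the treatment of NAFLD, compared with metformin and simvastatin".

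Protocol IV.2.4 treats as lost to follow-up "patients who need to take other medications due to the development of other new diseases". It limits this to medicines that could affect the results, and its example is glucose-lowering drugs, insulin among them.

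**The concern.** A safety population should hold everyone who was exposed and observed. Taking a prohibited drug is not a baseline characteristic. It normally happens during treatment, and one reason for it is that the patient became ill and needed another medicine. Removing patients on that basis selects on something the outcome can cause.

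The loss is not limited to events after the drug. The whole patient leaves, so an event recorded weeks before the drug also disappears.

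The rule also runs in an odd direction. It can keep an over-age patient, who should not have been enrolled, while it drops a treated patient because of what happened on treatment.

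What is at stake is the safety comparison with metformin and simvastatin. The SAP describes the trial as open-label, and the supplied text has no list of prohibited drugs. Whether a given medicine counts as prohibited may therefore be decided with the arm known, and exclusions may be unequal between arms. SAP 9.5 also describes baseline characteristics on the Safety Set, so the same selection would enter the baseline table.

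**Working it through.** **Step 1. Is the patient in or out?** Take a randomised patient who was dosed, had a safety assessment and then took a prohibited drug. The first sentence of SAP 6.3 puts the patient in. The later clause takes the patient out. SAP 6.2 also removes the patient from the Per Protocol Set. If such a patient counts as an exclusion case, SAP 6.1 removes the patient from the Full Analysis Set too. No other section brings these patients back into a safety analysis.

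**Step 2. Arm size, used only as a base for the illustration.** SAP 3.4 gives n = 44 and 10% loss: 44 / (1 − 0.10) = 48.9, rounded up to 49 per arm, and 4 × 49 = 196. This matches the plan.

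**Step 3. Formula.** Let N be dosed and assessed patients in an arm, A those with an event, k the users of prohibited drugs, and m the users with an event.

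- Full rate: A / N
- Rate with the clause applied: (A − m) / (N − k)

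The second is below the first when N(A − m) < A(N − k), that is, when m/k > A/N. So the rate falls if users had events more often than the arm as a whole, stays the same if they had them equally often, and rises if less often. For patients whose event led to the drug, m/k = 1; removing them alone always lowers the rate, unless every patient in the arm had an event.

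**Step 4. Numbers.** The documents give no adverse event rate and no expected number of users. A, k and m below are assumptions; N = 49.

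| A | Full rate | k | All users had an event | One user did | No user did |
|---|---|---|---|---|---|
| 5 | 5/49 = 10.2% | 2 | 3/47 = 6.4% | 4/47 = 8.5% | 5/47 = 10.6% |
| 10 | 10/49 = 20.4% | 2 | 8/47 = 17.0% | 9/47 = 19.1% | 10/47 = 21.3% |
| 10 | 10/49 = 20.4% | 5 | 5/44 = 11.4% | 9/44 = 20.5% | 10/44 = 22.7% |
| 15 | 15/49 = 30.6% | 5 | 10/44 = 22.7% | 14/44 = 31.8% | 15/44 = 34.1% |

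For A = 10 and k = 5 the break-even is m = 5 × 10/49 = 1.02, which is why one event among five users leaves the rate almost unchanged.

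**Step 5. Between arms.** Suppose two arms both have 10 of 49 patients with an event. One has 5 users, all with an event; the other has no users. The reported rates are 11.4% and 20.4%, an apparent difference of 9.0 percentage points where there is none. These counts are also assumed.

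**The case against.** The strongest reply is about grammar. The disputed clause ends a sentence about which excluded cases may still be evaluated. It can be read as limiting only that re-admission: over-age cases may come back, prohibited-drug cases may not. A dosed patient who was never an excluded case would then stay in under the first sentence. This reading is possible, so the documents do not establish that every user is certain to be dropped. It does not rescue the section, because the SAP never says whether a prohibited-drug user is an excluded case, and an analyst could apply either reading.

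A second reply is that Protocol IV.2.4 does not call its interfering medicines prohibited, and classes the patients who need them as lost to follow-up. This stands. That those medicines are the prohibited drugs of SAP 6.3 is an inference. The protocol does show that a new illness leading to an interfering medicine is foreseen.

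A third reply is that the direction of the bias is not fixed. This also stands, as Step 3 shows.

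A fourth is that the primary endpoint is the fat attenuation index, that the protocol's stated objective covers efficacy and intestinal function only, and that the efficacy result and sample size are untouched. That is true, but safety against the two comparator drugs is in the SAP's first primary objective.

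**Conclusion.** The point holds. SAP 6.3 contradicts itself, and if the clause is followed, observed events of treated patients are discarded for a post-randomisation reason that an adverse event can cause. The adverse event rate can then be biased. It is too low where adverse events led to the drug, and overall it is lower only if users' event rate exceeds the arm's. In the main illustration the reported rate lies between 11.4% and 22.7% against a full rate of 20.4%. The true size cannot be computed from the documents.

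This rests on two assumptions: that prohibited-drug use in SAP 6.3 means use during the trial, as SAP 6.2 says of banned substances, and that the event and user counts are as stated.

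A reader might go further and infer that the reported rate is bound to be too low, that serious events would be hit hardest, or that the comparison between arms would be reversed. The documents support none of these. The clause covers users whatever their reason for taking the drug, nothing in the text links seriousness to prohibited drugs, and there are no event figures from which a reversal could be shown. What is supported is that the bias can differ by arm and so distort the comparison.

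**What to change.** Delete "but will not include cases who use prohibited drugs" from SAP 6.3, so that every dosed patient with a safety assessment stays in the Safety Set and in the adverse event tables. Let prohibited-drug use affect the Per Protocol Set only, where SAP 6.2 already handles it, and report it as a protocol deviation. Optionally, add a listing or sensitivity table that marks events starting after the first prohibited drug.

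The cost is one SAP clause and, if wanted, one output. No new data are needed: SAP 9.4 already codes and lists concomitant drugs, and SAP 9.2 already lists important deviations by patient. The downside is that some later events may be due to the prohibited drug rather than the study treatment; the listing makes these visible. The deletion does not settle how the lifestyle-only arm, which receives no study drug, meets the one-dose condition; that is a separate question.
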